- ii. Statins: Statin therapy is associated with muscle issues that range from more minor issues of muscle pain, cramping and fatigue, to myopathies, to the very severe issues of rhabdomyalgia, although this is rare. Statins are the most prescribed drug in the world. Statins are also associated with headaches, nausea, and constipation. Statins are also not well tolerated by athletes suggesting that exercise may worsen the effects of statins on skeletal muscle. Thus, there is the potential that participants in our study may have adverse effects while taking statins. A recent trial conducted by our consultant, [name], utilized 80 mg/day of atorvastatin and found that ~15% of participants experienced pain and weakness (2). atorvastatin 80 mg is an increasingly common dose because three large clinical trials, REVERSAL (atorva 80 v. prava 40, n=502) (3), PROVE IT (atorva 80 v. prava 40, n=4,162) (4), and TNT (atorva 80 v. prava 10, n=10,001) (5) demonstrated reduced atherosclerosis and cardiac events with atorvastatin 80 mg. These studies were done in CAD patients, a group on multiple other medications and likely to be at higher risk for side effects than our healthy participants. Nevertheless, side effects were rare. Liver function test (>3 times upper normal limits [UNL]) and creatinine kinase (CK) elevations (> 10 UNL) occurred in only 1-3.3% of patients treated with atorvastatin 80 mg for up to 24 months, respectively. These side effects should be even more rare given that we will pre-screen and exclude individuals with polymorphisms (GATM and SLC01B1) that increase risk for myopathy. We will test both muscle enzymes (creatine kinase) and liver enzymes (ALT) to determine if statins are causing either muscle myopathies or liver injury. This testing will occur at baseline and at 1 month into taking statins. If enzymes are elevated, the subject will be taken out of the study for their own health. Finally, study physicians at both KUMC who commonly prescribe statins and deal with patients who experience statin induced problems will provide medical coverage for our studies. Participants are free to abstain from taking their statins and leave the study at any time. Importantly, most individuals report that statin induced complications go away very quickly after stopping the therapy. Participants who are discontinued from the study for a medical reason judged to be appropriate by the study doctors will receive the same reimbursement as if they completed the study to avoid the possibility that a subject would "soldier on" simply for the reimbursement.
- iii. Muscle Biopsies: Acute issues of muscle tightness, soreness, and bruising can be associated with muscle biopsies. More severe problems include the risk of infection. To avoid these issues the biopsy procedures will be conducted with sterile techniques with medical supervision. Moreover, the participants are given detailed instructions including how to take care of the incision site and who to contact should anything seem abnormal.
- iv. IVGTT Catheter Placement and Venipuncture: Their risk is very minimal. However, certain risks including discomfort, blood clot, minor bleeding, bruising, infection,

and redness can occur. Aseptic techniques will be used to minimize such risks. Risks of bruising and minor pain can occur with venous phlebotomy. Venous catheter placements can rarely cause bleeding, bruising, soreness, and infection. Risk of bleeding after removal of the line also is possible. Infusion of glucose or insulin may cause the subject to feel nauseous or flushed. Drinks and snacks will be available for the participants at the completion of the IVGTT should they have low blood sugar or feel nauseous.

- v. DEXA: The DEXA scan may make participants slightly uncomfortable because you have to hold very still. This research study involves exposure to radiation equal to the radiation that most Americans receive in about 2 days from background radiation, such as naturally occurring radioactivity in the soil and air. The risk from radiation exposures of this magnitude is too small to be measured directly and is considered to be very low when compared with other everyday risks.
- b. Potential Benefits: All participants will gain health information about themselves. At the end of the study, results collected will be shared with the subject in face-to-face meetings. Moreover, although we are studying the impact of statins on muscle health, statins overall do have a strong track record of lowering blood lipids and in most trials lowering cardiovascular risk. Moreover, the health information gained throughout the study will aid the participants in making future medical decisions with their physicians in relation to cardiovascular and diabetes risk.
 In summary, the benefits to the participants are substantial, and the information detailing the impact of statins on mitochondrial, metabolic, and cardiovascular function have the promise of helping millions of patients and physicians evaluate the risk to benefit ratio of statin therapy. There are risks associated with the study, but the experience and medical expertise of the research team should keep these at a minimum, and our track record with exercise and diet research indicates that this diligence has been effective.
- G. Location where study will be performed: All portions of the study will occur at KUMC.
- H. Collaboration: This is a Multi-PI application from Drs. [name] and [name] from the University of Kansas Medical Center and East Carolina University, respectively. Both investigators have been conducting research on statins for several years. The project was born out of a common desire to combine their individual expertise to investigate the mechanisms underlying skeletal muscle complications associated with statin therapy in a repeated measures, longitudinal design. Due to the scope of the design (i.e., number of participants, duration) and complexities of the primary outcome measures, it was felt a multi-PI, multi-institutional approach represented the most efficient and statistically valid means of completing the project and thereby making truly sustained impact of the field. Each investigator has trained at/frequently visited the other institute and is quite familiar with the research environments. Standard operating procedures will be developed for all common testing and primary outcome measurements, and each investigator and their key personnel will visit the other institute prior to commencing the study to conduct trial runs to insure continuity. The PIs will share responsibility for fiscal and research management. Using the multi-PI approach with two investigators with translational research experience and

complimentary analytical expertise dramatically increases the power of the study and the likelihood of successfully completing the proposed aims.

I. Single IRB Review for a Multi-site study: NA

J. Personnel who will conduct the study, including:

- 1. Indicate, by title, who will be present during study procedure(s): PI, Study Coordinator
- 2. Primary responsibility for the following activities, for example:
 - a. Determining eligibility: PI, Study Coordinator
 - b. Obtaining informed consent: PI, Study Coordinator
 - c. Providing on-going information to the study sponsor and the IRB: PI, Study Coordinator
 - d. Maintaining participant's research records: PI, Study Coordinator
 - e. Completing physical examination: PI, CTSU Nurse
 - f. Taking vital signs, height, weight: CTSU Nurses
 - g. Drawing / collecting laboratory specimens: CTSU Nurses
 - Performing / conducting tests, procedures, interventions, questionnaires: PI,
 Study Coordinator
 - i. Completing study data forms: Study Coordinator
 - j. Managing study database: PI

K. Assessment of Subject Safety and Development of a Data and Safety Monitoring Plan

- **a. Key personnel:** [name], [name], [name], [name], study physician at KUMC and [name], study physician at ECU.
- b. Plan for safety monitoring and review: [name] will serve as the Chair of the Data Safety Monitoring Board and will convene every 6 months with the other members, Drs. [name] and [name] to make decisions on safety of the participants. Enrollment data will also be reviewed twice a year by the DSMB. In addition, data will be reviewed on a yearly basis with the biostatistician, [name] to determine if the studies should be shortened do to either no measured effect or due to effects that are greater than what power calculations indicated. If problems occur with participants, blinded study staff will alert [name]. [name] will have access to dose and type of statin and will consult the study physicians/cardiologist to make a decision on whether the subject should be removed from the study for safety concerns. The PI and other key personnel will be examining research data on a subject to subject basis to ensure it is accurate and to address any potential problems that may arise with the protocols. In addition, Drs. [name] and [name] will discuss data at least once per month through in person meetings or by phone to ensure that data collection is occurring in a consistent manner at both locations.
- **c. Plan for adverse event reporting:** Adverse events will be defined as any untoward medical occurrence in study participants or others immediately involved in the

performance of the protocol, which does not necessarily have a causal relationship with the study treatment, but results in a change in intervention, daily function, hospitalization or rated category 3 or above using the National Cancer Institute Common Terminology Criteria for Adverse Events (CTCAE) v3.0. Expected events such as slight muscle soreness consistent with statin therapy, or those consistent with a participant's prior medical history not sufficient to alter the intervention will not be considered an AE. Staff involved in performance of the protocol (e.g. coordinators) will continually monitor participants for adverse events throughout the intervention, and study staff will assess adverse events at every testing visit as well as during regularly scheduled telephone assessments with all randomized participants.

If study staff, tester, or participant reports adverse events or complaints, relevant information will be collected and documented. The participant will be evaluated by the unblinded investigator identified in the protocol. The investigator will determine the severity (according to the CTCAE) and relatedness of the AE to the intervention. The investigator will identify adverse events of clinical concern, those that may require further workup, or suggest that additional participation in the intervention might be a safety risk. These AEs will first be discussed with the participant and then communicated to the study staff or providers with participant's consent and as appropriate. Serious adverse events directly related to the intervention will be reported immediately to the IRB. Any adverse event rate over 30% in 12 months will be reported to the NIH.

III. Subject Participation

A. Recruitment:

- a. Participants will be recruited from the KUMC campus, from hospitals and clinics associated with KUMC and metro-Kansas City, Kansas and Missouri areas. Study team will also use BPA system through Epic to recruit participants. Recruiting will occur through physicians and clinics and through advertisements in emails, flyers, newspaper ads, radio spots, etc. Interested participants will call or email and undergo initial phone screening, conducted by trained study staff, to see if they qualify. Should they meet the initial qualifications, they will come to the lab for an informed consent meeting with the PI, research coordinator, or other study staff. They will then be provided with an informed consent that is fully approved by the IRB at KUMC to review prior to the inperson meeting. Participants who are interested in taking part in the study will be asked to sign the informed consent in the presence of a witness. Participants will have adequate opportunity to review the informed consent and to ask any questions they may have about the research protocol, compensation, risks, and benefits of taking part in the study.
- **b.** The targeted/ planned distribution of participants by sex/gender and racial/ethnic groups for the proposed study or protocol will follow the local demographics. The Kansas City area has a population that is comprised of 13 % African American, 2% Asian, 5% Hispanic, and 80% Caucasian. It is anticipated that the study population at KUMC will have much the same racial and ethnic make-up. Statistical comparisons among minorities or between minority and Caucasian groups are not aims of the current study. We fully intend to enroll every eligible minority individual in these studies. Ample pools of all targeted populations exist.

- **c.** Selection criteria: It is anticipated that women will comprise approximately 50% of the study participants. It is also anticipated that gender will not be a significant factor in the response to exercise training or statin therapy, and hence, it is anticipated that the data from both genders will be compiled and analyzed as a group.
- **d.** Exclusions: No minority groups will be excluded.
- **e.** Outreach: The subject pool will be limited to the greater Kansas City (MO and KS) area. Subject will need to make regular visits to the laboratories, and thus, participants will only be recruited who are within the county region and can regularly make appointments.
- B. Screening Interview/questionnaire: NA
- C. Informed consent process and timing of obtaining of consent: Should the participant meet the initial qualifications, they will come to the lab for an informed consent meeting with the PI, research coordinator, or other study staff. They will be provided with an informed consent that is fully approved by the IRB at KUMC to review prior to the in-person meeting. Participants who are interested in taking part in the study will be asked to sign the informed consent in the presence of a witness. Participants will have adequate opportunity to review the informed consent and to ask any questions they may have about the research protocol, compensation, risks, and benefits of taking part in the study.
- **D. Alternatives to Participation:** NA
- **E.** Costs to Participants: There is no cost to participants for participation in this study.
- **F.** How new information will be conveyed to the study subject and how it will be documented: New information about risks associated with involvement in the study will be disseminated but no other information will be disclosed.
- **G. Payment, including a prorated plan for payment:** Participants will receive a one-time compensation of \$600 for completing all study visits. If participation ends early, participants will receive \$75 for each study visit excluding screening. They will be given a ClinCard, which works like a debit card. After completion of the study, payment will be added to the card by computer. The money will be available within 1 business day. Participants can use the ClinCard at an ATM or at a store. Study staff will collect their name, address, and social security number to allow them to set the participant up in the ClinCard system through the KUMC Research Institute. Study payments are taxable income. A form 1099 will be sent to the subject and the Internal Revenue Service if your payments are \$600 or more in a calendar year. The participants' personal information will be kept on a secure computer. It will be removed from the computer after the study is over and the money on the card has been used. The information will not be shared with other businesses. It will be kept confidential.
- **H. Payment for a research-related injury:** We will include the following text in the consent form: "All forms of medical findings, whether routine or experimental, involve some risk of

injury. In spite of all safety measures, you might develop medical problems from participating in this study. You must report any suspected illness or injury to the study coordinator immediately. If such problems occur, you will be provided with emergency medical treatment and the investigator will assist you in getting proper follow-up medical treatment. Neither the investigator nor the sponsor will provide compensation for research-related injuries. Payment of lost wages, disability or discomfort is not available. You do not give up any of your rights by signing this form."

IV. Data Collection and Protection

- A. Data Management and Security: All identifiable files, data, and tissue will be coded and stored in secure locations. These data include: study progression, subject numbers, percent completion, data quality, subject retention, adverse events, etc. The PIs at both KUMC and ECU will be responsible for the quality of the data and will supervise the data acquisition with the help of study coordinators. All data will be coded for confidentiality, and only the PI, study coordinator, and study statistician will have access to the code. The results of each test on each subject will be screened by the study coordinator prior to entering on the spreadsheet. This is standard practice in our laboratories. Hard copies are kept in dedicated locked cabinets. Specific coded subject files will be sent to the study statistician for statistical analyses. These analyses will be sent to the PI and study coordinator for dissemination to appropriate co-Is. At the end of participation in the study, each subject will receive a personal data summary of their test results. The study coordinator or a study investigator will discuss the results with the subject. After 1 year, the PI's including the biostatistician, [name] will be un-blinded but the study staff will remain blinded, so that the important research findings can begin to be delineated. This will also allow for [name] to being to examine if the trial is finding more or less significant effects for outcome measures.
- **B. Sample / Specimen Collection:** All participants will be assigned a data code. Blood and tissue samples will be labeled with the participant's data code and stored in a locked freezer. Blood and tissue samples will be stored indefinitely following completion of current project for future research.
- **C. Tissue Banking Considerations:** Following completion of the current project, remaining blood and tissue samples will remain in locked freezer indefinitely. Samples will only be used by investigators of the current project, both KUMC and ECU, when a new biomarkers or techniques of interest emerge.
- **D. Procedures to protect subject confidentiality**: Risks to confidentiality are reduced by assigning all participants to a data code. Folders are stored in locked file cabinets, and only the PI and study coordinator have access to the locked files. Individual names or initials are not used in any discussions or publications of the data.
- **E. Quality Assurance / Monitoring:** Data will be reviewed twice a year by the Board Chair. In addition, data will be reviewed on a yearly basis with the biostatistician, [name] to determine if the studies should be shortened do to either no measured effect or due to effects that are greater than what power calculations indicated. The PI and other key

personnel will be examining research data on a subject to subject basis to ensure it is accurate and to address any potential problems that may arise with the protocols. In addition, Drs. [name] and [name] will discuss data at least once per month through in person meetings or by phone to ensure that data collection is occurring in a consistent manner at both locations.

V. Data Analysis and Reporting

- A. Statistical and Data Analysis: This project is a two-factor study. One factor is treatment group (between participants) and a second factor is time of data collection (0, 1, 6, and 12 months) (within subject). The data analysis will be carried out for the primary outcome variable of mitochondrial respiration in addition to other outcome variables (VO₂peak and insulin sensitivity, etc.). For each measure, its baseline measure and age will be added as covariates to adjust for the individual difference at baseline. Two-way interaction between treatment and time will be added in the model for testing if the outcome changes differently between groups over time. Additional variables, such as demographics, BMI, physical activity, etc. may also be included as covariates. If the test of trend difference is significant, then the comparison at each time point will also be considered to identify when the difference between groups reaches the maximum. Least Square Means will be used for the aforementioned comparisons. The statistical analysis will be performed with mixed procedure in STATA 13.1 (StataCorp LP, College Station, TX). Mixed model does not require complete data for a longitudinal study. Residual analyses will be conducted and efforts to address those will be made, including appropriate transformations.
- B. Expected Outcomes: Atorvastatin therapy will induce a progressive decline in skeletal muscle mitochondrial respiratory capacity that will be evident both in vivo (i.e., whole muscle NIRS) and in situ (i.e., respirometry in permeabilized fiber bundles). Based on the rationale outlined above and our preliminary data, we anticipate mitochondrial function will decline in a dose x time-dependent manner, occurring sooner in the high- verses low- dose treatment group. We further predict that the effect will be inversely related to the initial mitochondrial respiratory capacity of the skeletal muscle. Loss of mitochondrial functional capacity/content is predicted to, in turn, compromise the ability to maintain cellular redox homeostasis. Based on our previous findings (61), a shift to a more oxidized cellular redox state in skeletal muscle is expected to negatively impact insulin action. We also anticipate mitochondrial Ca2+ retention capacity will be reduced by statin therapy, providing a potential mechanism for the loss of mitochondrial content over time. If this occurs, follow up measures of genes and proteins controlling Ca2+ retention capacity (mitochondrial calcium uniporter and antiporter), and apoptosis and mitophagy (Bcl-2 (anti-apoptotic)/Bax (proapoptotic) will be performed to determine if these pathways are altered by low or high dose statins. Consistent with the reductions in mitochondrial function, we expect whole body insulin sensitivity and cardiorespiratory fitness (VO2 max) to also be reduced in a dose and time dependent manner (i.e., downstream of declines in mitochondrial function) in response to statin therapy. Of particular interest will be to determine whether reductions in mitochondrial respiratory capacity are associated with lower pain threshold and higher CK levels at rest and/or in response to exercise testing, and whether such changes are associated with compromised indices of cardiovascular function (increased heart rate and/or

reduced stroke volume), potentially occurring secondary to mitochondrial dysfunction in skeletal muscle or in another cell type like endothelial cells. Most of the data, since it is collected in real-time, will be analyzed as the study progresses allowing us to stop the study early should statistical differences in the primary outcome measures be detected prior to completion.

- **C. Study results to participants**: At the end of participation in the study, each subject will receive a personal data summary of their test results. The study coordinator or a study investigator will discuss the results with the subject. Results to be shared include: Body composition, exercise testing results, lipid profile, liver function (ALT), and glucose and insulin results from IVGTT, and summary of physical activity levels.
- D. Publication Plan: We will publish all data derived from this award in a timely fashion and to make those data freely available to the general research community whenever possible. All genomic data will be made publicly available through NCBI's Gene Expression Omnibus (GEO), and all publications that result from this work will be deposited in PubMed Central (PMC).

VI. Bibliography / References / Literature Cited

- 1. Wilson TM, and Tanaka H. Meta-analysis of the age-associated decline in maximal aerobic capacity in men: relation to training status. Am J Physiol Heart Circ Physiol. 2000;278(3):H829-34.

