- iv. Fasting Blood Draw: Glucose, insulin, total cholesterol, HDL-C, LDL-C, triglycerides, creatinine, CK, and ALT will be measured in fasting blood samples.
- v. Insulin Sensitivity: Glucose and insulin, and insulin sensitivity will be calculated using a minimal model program following the IVGTT.
- vi. Cardiovascular Function: Heart rate and stroke volume (and finometer) will be measured under resting conditions.
- **B. Study Type and Design:** This study is a longitudinal, repeated measures, double-blinded design with participants randomly assigned to placebo, low (20 mg/d) or high (80 mg/d) atorvastatin therapy for a one year dose-response study. We expect to screen approximately of 500 participants to enroll (randomize) a maximum of 60 participants. The goal is to have 45 participants complete all study procedures (15 in each group). Repeated measures design allows each subject to serve as their own control. Placebo groups are included to account for potential changes in muscle mitochondrial function independent of statin therapy over the 1 year dose-response.

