- C. Sample size, statistical methods, and power calculation: The randomization for study drugs will be carried out by the biostatistician using a computer-based random number generator at a 1:1:1 allocation. Sample size for study is powered on the basis of detecting a difference in mitochondrial respiratory function, the primary outcome measure, between three groups (e.g., placebo, and 20 or 80 mg/d atorvastatin therapy) at 12 months posttreatment. Our pilot study of statin effect on maximal ADP-stimulated O2 consumption rate (JO_2) after 56 days based on 8 participants showed a mean change of 88.5 (pmol/sec/mg) with standard deviation of 59.9 (pmol/sec/mg), which can be standardized into a very large pre-post effect size of -1.48 (Cohen's d). All of these 8 participants experienced a decrease of 11.13% to 66.94% in 56 days, suggesting the decreasing trends are very consistent among participants. The overall decreasing trend of maximal ADP-stimulated O2 consumption rate across all time points also suggests that the decreasing trend will continue beyond 56 days. For the other outcomes variables, insulin-sensitivity and in-vivo O2 recovery kinetics (NIRS), only measurements at baseline and day 56 are available and the observed changes are -0.65 (1.20) (mU/L)⁻¹ min⁻¹ and 19.07 (21.80) mVO₂, which can be standardized into effect sizes of -0.54, and 0.87, respectively. In a much longer study period of 12 month, the within group changes for these variables are expected to be greater. Expecting no change or a small change in the placebo as well as the low-dose group, our primary analyses are two subgroup comparisons: high-dose vs. low-dose and high-dose vs. placebo and the two expected between-group effect sizes (high-dose vs. low-dose and highdose vs. placebo) are large (close to the within-group effect sizes in the pilot data). With 27 participants in each group, a two-sided two sample t-test has 80% power of detecting an effect size of 0.87 (Cohen's d) at 0.025 level to maintain the overall type I error rate at 0.05 level for the two group comparisons. We will recruit 30 participants for each group to allow

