for 10% dropouts. The subject enrollment will be split equally between the two sites (15 participants/group per site). For this study, our primary analysis is to use mixed model to test the interaction between group and time, which is expected to be more powerful than the two-sample t-test because all repeated measurements will be considered in modeling, baseline patient characteristics can be controlled statistically, and participants with missing data can be included for analysis.

D. Subject Criteria

a. Inclusion criteria/Exclusion criteria:

- i. Inclusion Criteria
 - Ages 35–65 years
 - BMI between 25-43 kg•m²
 - >5% risk for a cardiovascular event in the next 10 years according to the 2013 American College of Cardiology/American Heart Association risk calculator and/or 2 out of 5 metabolic syndrome risk factors (Triglycerides ≥ 150 mg/dL; HDL ≤ 40 mg/dL; Glucose ≥ 100mg/dL; Waist Circumference ≥ 102cm for males, 88cm for females; Blood pressure: ≥ 130mmHg systolic and/or 85mmHg diastolic or being treated for hypertension) and/or LDL-Cholesterol >120 mg/dl.
 - Stable doses of medications for 90 days
 - Willing to stop all NSAIDs and aspirin for 7 days prior to muscle biopsy

[figure not shown]
ii. Exclusion Criteria

- Smoking
- Previous use of statins
- Use of other medications or supplements that affect lipid profiles or body weight in the last 6 months
 - o e.g., fibric acids, bile acid sequestrants, nicotinic acids, fish oil
- Diagnosis of chronic diseases including CVD, other metabolic diseases (e.g., thyroid), current diagnosis and active treatment of cancer, HIV, or acquired immunodeficiency syndrome.
- Diagnosis of type 1 or type 2 diabetes at the time of screening (fasting blood glucose >126mg/dL). If evidence of type 2 diabetes outcome measures is detected during the course of the study (fasting glucose > 126 mg/dl or HbA1c > 6.5%) we will notify the participant to contact their physician.
- History of abnormal bleeding problems
- Currently taking (within the last 10 days) anti-platelet medication (Plavix), Warfarin, and other anti-coagulants (eliquis, pradaxa, and xarelto) medications.
- >2 fold upper normal limit (UNL) for ALT or creatinine
- Women who are pregnant or breastfeeding
- Individuals with polymorphism (SLCO1B1) known to be associated with susceptibility for statin induced myopathies (tested at screening)
- Currently enrolled in another research study

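### The 80% power in II.C rests on 27 analysed per group, but II.B caps randomisation at 60 and aims for 15 completers per group, where the same calculation gives 51% to 66%

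*Combined protocol and SAP*

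**What the plan says.** Section II.B (Study Type and Design) plans "to enroll (randomize) a maximum of 60 participants" and adds: "The goal is to have 45 participants complete all study procedures (15 in each group").

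Section II.C (Sample size, statistical methods, and power calculation) gives the only quantified power claim: "With 27 participants in each group, a two-sided two sample t-test has 80% power of detecting an effect size of 0.87", at a two-sided level of 0.025 for each of two comparisons (high dose against low dose, and high dose against placebo). It recruits 30 per group to allow for 10% dropout, and continues: "The subject enrollment will be split equally between the two sites (15 participants/group per site"). Allocation is 1:1:1.

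On the outcome, II.C states: "Sample size for study is powered on the basis of detecting a difference in mitochondrial respiratory function, the primary outcome measure". The respiration pilot effect is given as -1.48. For insulin sensitivity and NIRS, the pilot changes are reported as values "which can be standardized into effect sizes of -0.54, and 0.87, respectively".

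On location, II.G states: "All portions of the study will occur at KUMC". Section III.A limits recruitment to greater Kansas City. Section II.H, however, says that "it was felt a multi-PI, multi-institutional approach represented the most efficient and statistically valid means of completing the project", and II.K, IV.A and IV.E still refer to two institutions or two locations.

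**The concern.** A reader who combines II.B and II.C will attach 80% power to a trial of 60 randomised participants. That power belongs to a trial of 90. If the cap of 60 stands, a null result could be taken as evidence against a between-group effect of 0.87 with 80% power, when the sizing test gives much less.

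The mismatch also affects the conduct of the trial. II.K and IV.E plan yearly reviews of whether to shorten the study, partly by comparing observed effects with the power calculation. Those reviews need a calculation that matches the sample being enrolled.

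A second ambiguity lies in the effect size. II.C says the trial is sized on mitochondrial respiration, but the 0.87 it uses equals the pilot value for NIRS, a secondary objective in II.A. No reason is given for the choice.

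**Working it through.** **Inputs.** From II.C: two-sided two-sample t-test, alpha 0.025 per comparison, d = 0.87, 27 analysed per group, 30 recruited per group, 10% dropout, 1:1:1 allocation. From II.B: at most 60 randomised, 45 completers.

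**Sample sizes side by side.**
- II.C: 3 × 30 = 90 recruited; 30 × 0.9 = 27 per group analysed.
- II.B: 60 / 3 = 20 per group at most; 45 / 3 = 15 completers per group.
- 90 exceeds the cap by 30. Loss implied by cap and goal in II.B: 1 − 45/60 = 25%, against 10% in II.C.

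**Source of the effect sizes.** Respiration: 88.5 / 59.9 = 1.48. NIRS: 19.07 / 21.80 = 0.87.

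**Power formula.** With n per group, df = 2n − 2, noncentrality λ = d√(n/2), and c the 0.9875 quantile of t on df degrees of freedom, power = P(T > c) + P(T < −c), where T is noncentral t(df, λ).

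**The plan's own figure.** n = 27, d = 0.87: λ = 0.87 × √13.5 = 3.197, c = 2.308, power 81.0%. At n = 26 it is 79.3%, so 27 is the smallest n that reaches 80%. II.C is arithmetically correct for its own sample.

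**The same test at the II.B sample.**
- n = 20: λ = 0.87 × √10 = 2.751, c = 2.334, power 66.2%.
- n = 15: λ = 0.87 × √7.5 = 2.383, c = 2.368, power 51.4%.

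| n per group | d = 0.87 | d = 1.48 | d = 0.43 | d detectable at 80% |
|---|---|---|---|---|
| 15 | 51% | 95% | 13% | 1.18 |
| 20 | 66% | 99% | 18% | 1.01 |
| 27 | 81% | 99.9% | 24% | 0.86 |

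The d = 0.43 column is the lower 95% limit for the respiration pilot effect. With n = 8, t = 1.48 × √8 ≈ 4.18 on 7 df; inverting the noncentral t gives an interval of about 0.43 to 2.48.

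**Two-site reading.** With 30 analysed per group, d = 0.87 gives 85%.

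**Baseline adjustment.** The documents give no within-person correlation ρ, so values are assumed. ANCOVA on 2n − 3 df was averaged over chance baseline imbalance, with residual SD reduced by √(1 − ρ²). If d is scaled on the month-12 SD σ, the difference is 0.87σ. If it is scaled on the change-score SD, the difference is 0.87σ√(2(1 − ρ)).

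| n per group | d scaled on | ρ = 0.3 | ρ = 0.5 | ρ = 0.7 |
|---|---|---|---|---|
| 15 | change SD | 70% | 63% | 57% |
| 15 | month-12 SD | 54% | 63% | 81% |
| 20 | change SD | 84% | 78% | 73% |
| 20 | month-12 SD | 69% | 78% | 92% |

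Ignoring chance imbalance at ρ = 0.5, adjusted d = 0.87 / √0.75 = 1.005, which gives 65% at 15 and 80% at 20. The figures for 20 are upper bounds, because participants who drop out contribute only partial data.

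**The case against.** The strongest objection is that 51% and 66% are not power for the primary outcome. They use the NIRS effect, and II.C expects between-group effects close to the pilot values. At the respiration value of 1.48, moving from 27 to 15 per group lowers power only from 99.9% to 95%. This stands: the figures show that the stated claim fails, not that the primary objective is underpowered. But 1.48 is an uncontrolled 56-day change in 8 people, and II.C itself chose not to size on it. The poor power at its lower limit comes from the small pilot rather than the cap, since 27 per group would give only 24% there.

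Next, the t-test is only the sizing device. The primary analysis is a mixed model that adjusts for baseline and keeps participants with missing data, so 51% is an unadjusted, completers-only figure. That also stands. The protocol does not quantify the gain, however, and over the assumed correlations it may or may not restore 80%.

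Third, II.B may describe only the Kansas share of a two-site trial, since its 15 per group matches the per-site number in II.C; power would then be about 81% to 85%. This does not reconcile the sections. II.C enrols 45 per site, whereas II.B enrols up to 60 and has 45 completing. The reading also conflicts with II.G. The not-applicable entry for single-IRB review in II.I is weak evidence either way.

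Finally, the 25% is inferred from a cap and a goal and is not a stated dropout assumption. That is right, and the protocol should state one.

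**Conclusion.** The concern holds. II.B and II.C give sample sizes that cannot both be followed, and the site count is unsettled across II.C, II.G, II.H, II.K, III.A, IV.A and IV.E. If the cap of 60 stands, the protocol's only quantified power claim does not apply to its sample: for d = 0.87 the sizing test has 51% power at 15 per group and 66% at 20, not 80%. With baseline adjustment the range is about 54% to 81% at 15 and 69% to 92% at 20, for assumed correlations of 0.3 to 0.7 and either scaling of d. For the respiration pilot effect of 1.48, power is 95% and 99%, subject to that estimate's wide interval. If the two-site plan stands, II.C's power is sound and II.B and II.G are the sections in error.

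**What to change.** Decide which design is current, then bring II.B, II.C and II.G, and the two-institution wording in II.H, II.K, IV.A and IV.E, to one sample size, one stated loss rate and one site count.

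If the cap of 60 with 15 completers per group stands, replace the 80% sentence in II.C with:
- unadjusted power at 15 and 20 per group for d = 0.87 (51%, 66%) and for d = 1.48 (95%, 99%, with the pilot interval of about 0.43 to 2.48);
- the outcome each effect size comes from, and the SD it is scaled on;
- any gain from the mixed model, shown as a range over stated correlations.

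If the two-site plan stands, correct II.B and II.G instead, and align the single-area recruitment text in III.A.

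The cost is protocol wording only. No extra enrolment is proposed. Under the cap of 60, the stated power becomes less favourable.
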